Participants will take daily olanzapine as the antipsychotic medication, Zyprexa Zydis. On the first day of medication each participant will take Zyprexa Zydis 2.5 mg/day PO. Dose will be increased in the second day and participants will be taking Zyprexa Zydis 5 mg/day, PO, for the following days.

The medication will always begin on weekdays except Friday. On the 1st and 2nd day of the medication, participants will be asked to take the medication at McLean Hospital. After they take the medication we will monitor them closely for 1 hour to observe any side effects.

If the participants do not have any unacceptable side effects in the first two days, then they will be able to take the 13 remaining doses at home starting from the third day

On the 2nd, 5th, and 10th days of medication we will administer LUNERS (Liverpool University Neuroleptic Side Effect Rating Scale), ESRS (Extrapyramidal Symptom Rating Scale) and the Columbia Suicide Severity Rating Scale to assess potential side effects better. Weight and vital signs assessment, random blood glucose test will be done and ECG will be taken in these visits. On 5th, 10th, and 14th days all participants will have blood drawn for assessment of olanzapine plasma levels. Each visit will take about 30 minutes to an hour.

Participants' dietary intake will be assessed throughout the study using the 24-Hour Food Recall ASA24 at visits 3 and 8, and with the Food Craving Questionnaire-Trait-reduced (FCQ-T-r) at the 1st, 7th and 9th visits.

We will still complete the study with participants who miss up to 3 days of medication administration and qualify those participants as having received the intended course of medication (while recording their degree of noncompliance). Participants who miss more than 3 days of medication will be discontinued from the study.

3. **Endpoint Assessments:** All participants will undergo final investigations on the 15th and 16th days of the medication follow up period. The participants will take their last olanzapine dose on the evening of the 15th day. They will not be asked to take it on the 16th day as we plan to finish all final assessments during daytime and they take their medications in the evening. Participants will undergo 4T MR scan and neurocognitive testing on the 16th day. All other assessment and 3T MR scans will be done on the 15th day. The third part of the study will consist of the following procedures:
 - a. Clinical evaluation (60 minutes)

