 - b. Urine toxicology screen (5 minutes) and pregnancy test (5 minutes)
 - c. MRI procedure:
 - i. Common Anatomic Protocol (CAP) at 3T
 - ii. MRS protocol to quantify Glu and GABA at 3T
 - iii. Phosphorous MRS/MT at 4T
 - iv. Diffusion Tensor Spectroscopy (DTS) at 4T
 - d. Fasting (12 hours) blood draw of 20 mL (10 minutes)
 - e. Assessment of vital signs, weight, height, waist, and hip circumference (5 minutes)
 - f. ECG (10 minutes)
 - g. Neuropsychological Assessment (60-90 minutes)
 - i. MATRICS Consensus Cognitive Battery
 - h. 24-Hour food recall (Total Dietary Intake ASA24)

Medication: The half-life of olanzapine is 30 hours and one week would be sufficient to reach steady state. However, we decided to give medication longer than 1 week as we know that drug-induced adaptive changes take time to occur. Up until now, the longest duration of olanzapine use in healthy

volunteers has been 15 days. It is a randomized, PBO controlled, two- treatment (OLZ and PBO), crossover study in which the metabolic effects of olanzapine were investigated. 30 healthy men aged between 18-49 years underwent 10 mg/d olanzapine treatment for 15 days (5 mg/d for 3 days, then 10 mg/d for 12 days) in this study ¹⁵. There are also some other multiple-dose studies in which the participants were given daily olanzapine to investigate metabolic effects up to 15 days ^{16, 17, 18, 19}. None of the participants in these studies had major, severe side effects of olanzapine. Based on these studies we determined the duration of medication as 15 days in this study. We determined the daily olanzapine dosage as 5 mg in this study. We aimed to give healthy subjects only 5 mg/d olanzapine, the lower limit of the optimal dose range (5 mg ± 2.5 mg/d), to mimic the therapeutic effect but also protect the participants from adverse effects of treatment.

To assess the potential side effects of olanzapine, we set up 5 separate visits on the 1st, 2nd, 5th, 10th, 14th days of medication period. A physician will be present to monitor all participants' reactions to the medication and stop the medication if they are affected adversely.

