Nervous system side effects have frequently included somnolence, tremor, insomnia, dizziness, speech disorder, abnormal gait, amnesia, paresthesia, apathy, confusion, tremor, akathisia, hypertonia, articulation impairment, incoordination, abnormal dreams, emotional lability, agitation, nervousness, and hostility. Akinesia, alcohol misuse, antisocial reaction, ataxia, CNS stimulation, cogwheel rigidity, delirium, dementia, depersonalization, dysarthria, facial paralysis, hypesthesia, hypokinesia, hypotonia, incoordination, stimulant misuse, stupor, stuttering, tardive dyskinesia, vertigo, and withdrawal syndrome have also been reported. Circumoral paresthesia, coma, encephalopathy, neuralgia, neuropathy, nystagmus, paralysis, subarachnoid hemorrhage, tobacco misuse, and sleep related eating disorder have been reported rarely ^{22, 23, 24, 25, 26}. Almost all antipsychotics have been associated with a risk of epileptic seizure provocation. Olanzapine can lower seizure threshold. However, in patients on olanzapine for the treatment of a primary psychiatric disorder, clinical seizure is a rare occurrence. In most of these cases, a history of seizure or risk factors for seizures were reported.

All antipsychotics have been associated with the risk of sudden cardiac death due to an arrhythmia. In clinical trials, clinically meaningful QTc prolongations (Fridericia QT correction [QTcF] ≥ 500 milliseconds [msec] at any time post-baseline in patients with baseline QTcF < 500 msec) were uncommon (0.1% to 1%) in patients treated with olanzapine, with no significant differences in associated cardiac events compared to placebo.

Metabolic side effects have frequently included weight gain. Binge eating and increases in food craving have been associated with olanzapine. Additional studies have confirmed that patients receiving atypical antipsychotics are at an increased risk of developing hyperglycemia and/or diabetes mellitus.

Hepatic side effects have rarely included hepatitis, liver fatty deposit, and cholestatic or mixed liver injury. Transient and moderate, asymptomatic elevations in liver function tests have been reported.

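### Planned safety contact ends under 24 hours after the last olanzapine dose, leaving about 5.3 to 5.6 days of washout uncovered, and no later contact is stated for early stoppers (minor, cheap to fix)

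*Combined protocol and SAP*

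**What the plan says.** The Endpoint Assessments part of Research Design and Methods puts the final investigations on days 15 and 16. On dosing it says: "The participants will take their last olanzapine dose on the evening of the 15th day". On the last day it says: "Participants will undergo 4T MR scan and neurocognitive testing on the 16th day", and it adds: "They will not be asked to take it on the 16th day as we plan to finish all final assessments during daytime". The clinical evaluation, fasting bloods, vital signs and ECG belong to day 15.

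The Study Visits part sets visits on days 1, 2, 5, 10 and 14, with side-effect and suicidality scales on days 2, 5 and 10. It also says: "Participants who miss more than 3 days of medication will be discontinued from the study". Under Medication, a physician can "stop the medication if they are affected adversely". Participants may also withdraw whenever they wish. None of these routes out carries a stated exit assessment or later contact.

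Medication gives the kinetics: "The half-life of olanzapine is 30 hours". Foreseeable Risks and Discomforts includes, in a long list without rates, "vertigo, and withdrawal syndrome have also been reported". It also describes a very rare drug hypersensitivity syndrome with onset one to eight weeks after exposure. Data and Safety Monitoring ties close physician monitoring to the medication period, and staff checks to the time around each scan.

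**The concern.** Effects of stopping a drug appear as its level falls. Here almost all of that fall comes after the last scheduled contact. The participants are healthy and gain nothing therapeutic from olanzapine, so the plan should find out how they fare once it is withdrawn. As written, a withdrawal symptom in the following week reaches the study physician only if the participant volunteers it.

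The position of early stoppers is sharper. Someone whose drug was stopped because it was doing harm has no planned check that the harm has resolved.

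What is at stake is participant safety and the completeness of the adverse-event record. No efficacy or imaging estimate is involved.

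**Working it through.** **Inputs from the protocol.** Half-life 30 h (Medication). Last dose on the evening of day 15, final assessments finished in the daytime of day 16 (Endpoint Assessments). Two 4T scans of 90 minutes each (Baseline Assessments) and cognitive testing of 60-90 minutes (Endpoint Assessments).

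**Assumptions.** First-order elimination. Washout of five half-lives, a convention. Dose between 18:00 and 22:00. Day 16 starts no earlier than about 09:00 and ends by 17:00. Endpoint scans take as long as baseline scans.

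1. *The protocol's own kinetic statement.* It says one week is enough to reach steady state. 168 / 30 = 5.6 half-lives, and 1 - 2^(-5.6) = 97.9%. The statement reproduces.

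2. *Length of washout.* 5 x 30 = 150 h = 6.25 days, leaving 2^(-5) = 3.1% of the level. Counted from the evening of day 15, this ends about day 22.

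3. *End of contact on day 16.* The work listed takes 90 + 90 + 60 to 90 = 240 to 270 minutes, or 4-4.5 h. From a 09:00 start, contact ends at about 13:00 at the earliest.

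4. *Time from last dose to last contact.* Shortest: 22:00 to 13:00 = 15 h. Longest: 18:00 to 17:00 = 23 h. In half-lives, 15/30 = 0.50 and 23/30 = 0.77. The level remaining is 2^(-0.50) = 71% and 2^(-0.77) = 59%.

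5. *Washout without planned contact.* 150 - 23 = 127 h (5.3 days) to 150 - 15 = 135 h (5.6 days). With four half-lives (120 h) as the convention, it is 97-105 h (4.0-4.4 days).

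6. *Is a later visit implied anywhere?* Three baseline visits + five on-drug visits + two endpoint days = 10. The highest visit number named in the text is the 9th, so the numbering does not point to a visit after day 16.

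7. *What a call at 7 days covers.* 168 h is 5.6 half-lives, with 2.1% of the level left, so it falls after washout. It covers little of the hypersensitivity window:
   - Counted from the last dose, the window runs from day 15 + 7 = 22 to day 15 + 56 = 71, which is 50 calendar days. Of these, 71 - 22 = 49 fall after the call.
   - Counted from the first dose, it runs from day 1 + 7 = 8 to day 1 + 56 = 57, also 50 days. Of these, 57 - 22 = 35 fall after the call.

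   These are calendar days, not shares of risk. The documents give no onset distribution.

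**The case against.** The strongest reply is that risk is low and the plan manages it. The dose is 5 mg, at the bottom of the range the protocol regards as optimal. The duration was already used in volunteers at 10 mg, and of the earlier studies the protocol says: "None of the participants in these studies had major, severe side effects of olanzapine". Withdrawal syndrome has no rate attached, and hypersensitivity is called very rare. The uncontacted interval is about as long as the day 5 to day 10 gap accepted during home dosing. All of this stands, and it is why the point is minor. The difference is that a scheduled visit closes the day 5-10 gap, and nothing scheduled closes this one.

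A second reply is that the consent pages are not available and may tell participants what to report and to whom. That also stands, so the reporting reminder below is conditional. It does not fill the gap in scheduled contact: the visit schedule is visible, and spontaneous reports are not active follow-up.

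A third reply concerns early stoppers. Silence is not a plan to make no contact. The physician who stops the drug is already watching that person, and the investigator has general oversight. Someone discontinued after more than 3 consecutive missed days has already passed more than 72 h of the 150 h. This softens the point but does not supply a contact.

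A reader might infer more than the documents support:
- **That stopping olanzapine here raises suicidality.** No text links the two. Suicide attempts appear only among reported side effects, participants have no psychiatric diagnosis, and the Columbia scale is given on drug.
- **That the gap is 139 h.** This treats a 09:00 arrival on day 16 as the last contact, but the work that day takes 4-4.5 h.
- **That participants are poorly watched on drug.** The visits to day 14, the day-15 evaluation, ECG and bloods, and the staff checks around the day-16 scan show otherwise.
- **That abnormal day-15 ECG or laboratory results would be left alone.** The documents do not establish this.

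**Conclusion.** The point holds as a minor safety gap. The size rests on the 30 h half-life, the five-half-life convention and the assumed clock times. Other reasonable choices change the number of days but not the conclusion: any evening dose on day 15 with contact ending in the daytime of day 16 leaves most of the washout uncovered. For early stoppers the finding is only that no later contact is stated.

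Confidence is medium because the consent pages are unseen. The documents do not allow an estimate of how many events would be missed, and there may be none.

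**What to change.** Add one brief telephone call by existing staff about 7 days after the actual last dose. That is about day 22 for completers. For early stoppers, use the same timing, or call as soon as the stop is known. Ask about withdrawal symptoms, mood, unresolved side effects, fever and rash. State that the study physician follows up positive answers.

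Because the call covers little of the hypersensitivity window, remind participants at their last contact to report fever or rash until 8 weeks after the last dose (about day 71 for completers). This is needed only if the consent form does not already say so.

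The cost is a protocol amendment and up to about 30 short calls, with no new procedure. The last planned contact moves about a week later, and an occasional positive answer will need longer follow-up. The 8-week part still relies on self-report, and a call cannot detect organ involvement without symptoms.

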3. Without psychiatric diagnosis according to a structured psychiatric interview (SCID; First et al 1994).
4. Without history of a psychotic disorder among parents, siblings, or children.

Exclusion Criteria

1. Significant medical or neurological illness.
2. Unstable/active disease or potential contraindications.
3. Body mass index (BMI) greater than or equal to 30.
4. Taking any other medications, including over the counter supplements, with the exception of oral contraceptives for women.
5. Pregnancy. Females of child-bearing age must be using an effective contraceptive method.
6. History of smoking, substance abuse or dependence.
7. Contraindication to MR scan,
8. Medical condition that would prevent blood draws.

This study will be comprised of three main parts. The subject is free to withdraw from the study at any time. Similarly, the investigators may decide to stop the study if the purposes of the study cannot be met. All participants will be asked not to use alcohol or any other substances and drugs during the study period.

1. **Baseline Assessments:** The first part of the study will be carried out within 10 days of study entrance and consists of 3 separate visits which will take about 8 hours in total. This part of the study will consist of the following procedures:
 - a. Consenting procedures (20 minutes)
 - b. Clinical evaluation (120 minutes)
 - c. Urine toxicology screen (5 minutes) and blood pregnancy test (5 minutes)
 - d. MRI procedure:
 - i. Common Anatomic Protocol (CAP) at 3T (MR Scan at 3T – 1) (45 minutes)
 - ii. MRS protocol at 3T (MR Scan at 3T – 2) (30 minutes)
 - iii. Phosphorous MRS/MT at 4T (MR Scan at 4T – 1) (90 minutes)
 - iv. Diffusion Tensor Spectroscopy (DTS) at 4T (MR Scan at 4T – 2) (90 minutes)
 - e. Fasting (12 hours) blood draw of 20 mL (10 minutes)
 - f. Assessment of vital signs, weight, height, waist and hip circumference (5 minutes)
 - g. ECG (10 minutes)
 - h. Neuropsychiatric assessment (60-90 minutes)
 - i. MATRICS Consensus
 - i. 24-Hour food recall (Total Dietary Intake ASA24)
2. **Study Visits:** The second part of the study in which participants will take daily antipsychotic medication will be carried out within 15 days. There will be 5 separate visits on 1st, 2nd, 5th, 10th, and 14th days of medication and each visit will take about thirty to sixty minutes.

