MRI/MRS Scan: We have found that most subjects find that remaining in the scanner is somewhat uncomfortable but acceptable. An MRI technologist will be able to communicate with subjects at all times via intercom. Subjects are informed that they are free to stop at any point. Padding around the head will protect subjects from minor mechanical injuries and reduce head motion. Earplugs will be used to minimize the scanning noise of MR scanner. Women of childbearing potential must undergo a negative urine pregnancy test prior to completing the MR procedure on each day of MR scanning.

Women of childbearing age: Pregnant women and nursing mothers cannot participate to this study. If the participant is a woman of childbearing potential, she must be using a metal-free IUD, oral contraceptive, or barrier methods (*for at least 3 months*) or must be abstinent (*for at least 1 month: time to get the most reliable result with pregnancy test*) prior to this study. In addition, they must have a negative blood pregnancy test (*instead of urine pregnancy test*) at the beginning of the study.

Blood Draw: Subjects will be monitored for 15 minutes following the blood draw to ensure they are doing well. To minimize the possibility of bruising and infection from the blood draw, proper sterile phlebotomy techniques will be used.

Psychiatric Evaluation: Some subjects might feel uncomfortable answering questions during the psychiatric evaluation. They will not be forced to answer if they do not wish to answer any particular question.

Neuropsychiatric Assessment: Fatigue, frustration, or boredom may occur during the assessment; however, participants will be offered the option to discontinue testing or training sessions and resume at a later time in order to minimize these effects.

To minimize potential breach of confidentiality, subject data are coded with unique research numbers. The code linking the research number with personal identifiers is kept in binders separate from both clinical and imaging data and also in password- protected computer files on computers in a locked office at McLean. Subject interview records and imaging data are identified by research numbers and will be collected and stored via the secure web-based application REDCap. The application complies

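### No pregnancy test is tied to the first olanzapine dose, and no limit is set on the time from the last negative test to day 1

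*Combined protocol and SAP*

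**What the plan says.** All references are to the combined protocol and SAP, Research Design and Methods.

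- **Exclusion Criteria, item 5** excludes pregnancy and adds: "Females of child-bearing age must be using an effective contraceptive method".
- **Women of childbearing age** sets the contraception terms ("she must be using a metal-free IUD, oral contraceptive, or barrier methods", for at least 3 months, or else abstinence for at least 1 month). It continues: "In addition, they must have a negative blood pregnancy test", to be done when the study begins and specified as blood rather than urine.
- **Baseline Assessments** lists that blood test without assigning it to a particular visit. On timing it says: "The first part of the study will be carried out within 10 days of study entrance and consists of 3 separate visits".
- **MRI/MRS Scan** adds the scan-day rule: "Women of childbearing potential must undergo a negative urine pregnancy test prior to completing the MR procedure on each day of MR scanning".
- **Study Visits** gives the medication schedule: "There will be 5 separate visits on 1st, 2nd, 5th, 10th, and 14th days of medication". The first two doses are supervised: "On the 1st and 2nd day of the medication, participants will be asked to take the medication at McLean Hospital".
- **Endpoint Assessments** lists a further pregnancy test, with the final assessments on days 15 and 16.

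**The concern.** The protocol asks for a fresh negative result on the day of a scan but not on the day the study drug is first given. It gives no reason for the difference. Day 1 is the last point at which exposure can be avoided altogether. It is also a hospital visit, whereas doses from day 3 are taken at home.

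A woman who conceived shortly before or during baseline could test negative at baseline and be detectable by day 1. Under the current text nobody would be required to look. The participants are healthy volunteers with no treatment need to set against an avoidable exposure. The point concerns participant safety and enforcement of the protocol's own exclusion. It changes no endpoint, estimate or power figure.

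**Working it through.** The protocol states no figure to reproduce. The check sets every pregnancy-test provision beside the visit schedule.

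**1. What each test is tied to**

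| Test | Section | Tied to |
|---|---|---|
| Blood | Baseline Assessments; Women of childbearing age | Start of study |
| Urine | MRI/MRS Scan | Each scan day |
| Type not stated | Endpoint Assessments | Endpoint, days 15-16 |

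None is tied to the first dose.

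**2. What the medication visits contain (Study Visits)**

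- Days 1 and 2: supervised dose and 1 hour of observation.
- Days 2, 5 and 10: rating scales, weight, vital signs, random glucose and ECG.
- Days 5, 10 and 14: blood for olanzapine level.

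No pregnancy test is listed on any of the five days. No scan is listed on them either, so the scan-day rule does not supply one.

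**3. Whether any window caps the age of the last result at dose 1**

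The 10-day limit governs completion of baseline, counted from study entrance. The only rule on when dosing starts is that day 1 falls on Monday to Thursday. No text links the end of baseline to day 1. The maximum age of the last negative result therefore cannot be derived from the documents.

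**4. Illustration, on assumptions that are not in the documents**

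Suppose baseline takes the full 10 days and dosing starts on the next permitted day.

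- Wait from end of baseline to day 1: 1 day if baseline ends on Sunday to Wednesday, 2 if Saturday, 3 if Friday, 4 if Thursday. The range is 1 to 4 days.
- Blood test done on the day of entrance: 10 + 1 = 11 to 10 + 4 = 14 days old at dose 1.
- Urine test at a scan on the last baseline day: 1 to 4 days old at dose 1.

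A longer wait before day 1 would add to these figures day for day. An earlier last scan would also make the urine result older.

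**5. After dosing starts**

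The first listed test is on day 15, which is 15 − 1 = 14 days after the first dose. Doses are taken in the evening and the final assessments are done in the daytime, so a woman taking every dose would have had 14 (days 1 to 14) before that test.

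**The case against.** The strongest reply is that the risk is already largely handled. Before dosing, a woman of childbearing potential must have used contraception for at least 3 months or been abstinent for at least 1 month. She must also have a negative blood test and a negative urine test on every baseline scan day. Baseline holds four MR sessions (45 + 30 + 90 + 90 = 255 minutes), so at least one scan-day urine test is required before dosing. The abstinence period is expressly chosen with test reliability in mind, so the authors did think about detection timing. What is left is a pregnancy that becomes detectable between the last baseline scan and day 1 in someone who meets all of these conditions. No count of women, probability or pregnancy-specific olanzapine risk is available to size that.

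All of this stands, and it limits the point to a gap in timing. It does not close the gap, because each safeguard acts before day 1 by an interval the protocol leaves open. The reliability argument for abstinence also does not carry over to women who qualify through contraception.

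Three stronger readings are tempting and should not be drawn:

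- *Women could start olanzapine untested.* They could not: the blood test and the scan-day tests both come first.
- *The wait before day 1 is long.* No maximum is written, but nothing in the documents indicates a long delay. The absence of a limit is not itself a measure of size.
- *The visit numbers in the dietary schedule fix the wait.* Placing the food recall at visits 3 and 8 and the last craving questionnaire at visit 9 might suggest nine visits, with day 1 falling on the last baseline visit. That conflicts with the description of the baseline and medication visits as separate. It would also put the questionnaire on day 16, which is set aside for the 4T scan and cognitive testing. A ten-visit count does not fit fully either, since the second food recall would then fall on day 14 although it is listed at endpoint. No range for the wait can be taken from this.

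**Conclusion.** The point holds as a modest gap that is cheap to close. As written, no test confirms the pregnancy exclusion when exposure begins, and no limit applies to the age of the last negative result.

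The conclusion rests on reading the listed procedures as complete. If a site already tests on day 1, or happens to scan that day, the gap in practice is nil, but the protocol does not require either. The remaining risk is small and cannot be quantified from the documents. The day counts in the illustration depend on the assumptions stated there.

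**What to change.** Add to Study Visits, for day 1: women of childbearing potential must have a negative urine pregnancy test before the first olanzapine dose, and a scan-day test done that same day satisfies this. The result is then 0 days old at dose 1, whatever the wait after baseline. The 14 days to the day-15 test are unchanged.

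**Cost:** at most one urine kit and a few minutes per woman of childbearing potential. The ceiling is 30 × 1 = 30 kits if all 30 participants were such women. The 5 minutes shown at baseline is for a blood test, and the endpoint list gives 5 minutes without stating the test type, so neither is used here as a precise time for a urine test. No new visit is needed, because the first dose is already taken at the hospital.

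**Downside:** a positive or unclear result would delay or stop dosing for that participant, and a delay might mean rearranging her later visits.

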NCT02536846

Protocol Title: The effects of antipsychotic drugs on brain metabolism in healthy individuals

Protocol Version date: 4/5/21

PRINCIPAL INVESTIGATOR

[name], MD, PhD

[contact]

Schizophrenia & Bipolar Disorder Program

e-mail: [contact]

PROTOCOL TITLE

The effects of antipsychotic drugs on brain metabolism in healthy individuals.

BACKGROUND

Schizophrenia is a complex psychiatric disorder characterized by alterations in brain structure. It remains unclear yet whether some of these alterations may be related to pathophysiology of illness per se, or are the consequence of brain exposure to the effects of psychotropic drugs. In recent years evidence suggests that exposure to the effects of psychotropic drugs may contribute to some structural and other changes in brain. In this study, we aim to evaluate the effects of short-term antipsychotic medication use in healthy subjects on neuroimaging markers. We will also examine effects of antipsychotic exposure on neurocognitive performance.

The primary aim of this study is to investigate antipsychotic drug effects on brain energy metabolism in 30 healthy people by administering olanzapine over 15 days and using 31P MRS imaging at 4 Tesla. Secondary aims include studying the effects of olanzapine on other neuroimaging markers collected using MRI approaches and cognition.

We plan to study the levels of chemicals associated with cellular energy metabolism: kinetics of enzymes involved in cellular energy metabolism in brains of healthy people before and after use of antipsychotic drug olanzapine for 15 days. In addition, we will also collect data on the structure of the gray matter and white matter; resting state functional brain activity; levels of brain chemicals including glutamate and GABA; white matter integrity; and neurocognition. We will collect whole brain data where possible and focus on the medial prefrontal cortex and parietal cortex as two regions of interest whenever whole-brain data collection is not possible due to technical limitations.

RESEARCH DESIGN AND METHODS

Enrollment: The study will enroll up to 30 healthy people with no history of psychiatric illness or family history of psychosis.

There are no restrictions on subject recruitment based on sex, ethnic background or health status other than those mentioned below. Individuals who do not speak English will be excluded.

Inclusion Criteria

1. Age: 21-50 years old.
2. Male or female.

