with HIPAA regulations and will store the information securely, protected by web authentication, and Secure Sockets Layer (SSL) encryption. Dietary information captured from the ASA24 is stored in an NIH-designed database that is completely deidentified. The only document linking the participant's username and study number will be kept in a password-protected computer file in a locked office at McLean.

Statistical Analysis: There is no published literature on the effects of olanzapine on the brain measures we plan to study. Therefore, it is not possible to calculate a sample size that would detect a given between-group difference in this study. In fact, our hypothesis is that olanzapine administration does not cause significant abnormalities in brain metabolism. Therefore, we plan to recruit a sample that is large enough to establish the absence of a moderate or large effect. Our proposed sample size of 30 subjects will allow us to detect a difference with effect sizes of 0.45 or greater as significant at the $p<0.05$ level with 80% power. Note that effect sizes of 0.5 are generally considered moderate and 0.8 considered large. Therefore, a non-statistically significant finding with our sample size will suggest that any effects of olanzapine on brain metabolism are at best small. We will examine deviations induced by the study drug on brain metabolism using paired t-tests for before and after measurements.

FORESEEABLE RISKS AND DISCOMFORTS

In terms of olanzapine treatment, the medication may be unsafe for some people and cause some unwanted side effects (*neurological, gastrointestinal, dermatological, ocular, musculoskeletal, hematologic, endocrine, metabolic, psychiatric*).

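### The power statement (30 subjects, effect size 0.45, 80%) gives no sidedness or SD scale; as a two-sided paired t-test in SDs of change, power is 66% and the 80% detectable effect is 0.53, above the plan's own 0.5 benchmark

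*Combined protocol and SAP*

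**What the plan says.** All of the sample-size reasoning is in the Statistical Analysis paragraph of Research Design and Methods. The plan says no published data exist for these brain measures and hypothesises no significant abnormality. It therefore aims for a sample large enough to exclude a moderate or large effect. The power claim is "Our proposed sample size of 30 subjects will allow us to detect a difference with effect sizes of 0.45 or greater as significant", "as significant at the $p<0.05$ level with 80% power". The benchmarks follow: "Note that effect sizes of 0.5 are generally considered moderate and 0.8 considered large". From these the plan concludes that "a non-statistically significant finding with our sample size will suggest that any effects of olanzapine on brain metabolism are at best small". The analysis is given as: "We will examine deviations induced by the study drug on brain metabolism using paired t-tests for before and after measurements".

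Neither sidedness, nor the SD that defines the effect size, nor a before-after correlation is stated anywhere in the document. The Enrollment paragraph makes 30 a maximum: "The study will enroll up to 30 healthy people with no history of psychiatric illness or family history of psychosis". No allowance for incomplete pairs is given, although participants may withdraw, and those who miss more than 3 days of medication are discontinued.

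**The concern.** Without sidedness and scale, the 0.45 figure cannot be checked. The wording points to a two-sided test: it speaks of differences, deviations and any effects, and cites no earlier data that would give a direction. A paired t-test works on within-person change, so the SD of that change is the natural scale. Read this way, the claim of 80% power at 0.45 fails.

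The number carries weight because the expected result is null. The step from non-significance to small effects relies on 0.45 lying below the plan's moderate benchmark of 0.5. If the effect detectable with 80% power is above 0.5, that step loses its stated support, and a true moderate effect would be missed about one time in four (1 − 0.754 = 0.246).

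**Working it through.** **Inputs from the Statistical Analysis paragraph:** n = 30 pairs, effect size d = 0.45, alpha = 0.05, power 80%, paired t-test, moderate benchmark 0.5. Sidedness, SD scale and correlation are not given.

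**1. Reproducing the plan's figure.** For a paired test the normal approximation to the detectable effect is (z for alpha + z for power)/√n.

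- One-sided: (1.645 + 0.842)/√30 = 0.454. Power at 0.45 is 79.4%. This matches the stated 0.45 and 80%.
- Two-sided: (1.960 + 0.842)/√30 = 0.511. Power at 0.45 is 69.3%. This does not match.

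**2. Exact t-test, effect in SDs of change.** Power comes from the noncentral t distribution with 29 degrees of freedom and noncentrality d√30. At 0.45 the noncentrality is 0.45 × 5.477 = 2.465. The critical value is 2.045 two-sided and 1.699 one-sided.

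| | Two-sided | One-sided |
|---|---|---|
| Power at 0.45 | 66.4% | 77.7% |
| Power at 0.50 | 75.4% | 84.8% |
| Effect detectable with 80% power | 0.529 | 0.465 |
| Pairs needed for 0.45 | 41 | 32 |

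A simulation of 400,000 trials at 0.45 gave 66.5% two-sided and 77.8% one-sided. In the two-sided case, 40 pairs give 79.3% at 0.45 and 41 give 80.3%. For an effect of 0.50, 33 pairs give 79.5% and 34 give 80.8%.

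The one-sided test has about 0.003% power for a 0.45 effect in the untested direction.

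**3. Effect in baseline SDs, two-sided.** With equal SDs at both times and before-after correlation r, the effect in change SDs is d/√(2(1 − r)). The detectable d is therefore 0.529 × √(2(1 − r)). The document gives no r; the range below is an assumption.

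| r | Power at 0.45 | Effect detectable with 80% power |
|---|---|---|
| 0.2 | 47.0% | 0.67 |
| 0.5 | 66.4% | 0.53 |
| 0.6 | 75.9% | 0.47 |
| 0.64 | 80.2% | 0.45 |
| 0.8 | 96.5% | 0.33 |

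Solving for r: the detectable effect equals 0.45 at r = 1 − (0.45/0.529)²/2 ≈ 0.64, and 0.50 at r = 1 − (0.50/0.529)²/2 ≈ 0.55.

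**4. Incomplete pairs (illustration only; no dropout rate is given).** Two-sided and in change SDs, the detectable effect is 0.56 with 27 pairs and 0.60 with 24.

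**The case against.** The strongest reply is that no arithmetic error has been shown. A one-sided normal approximation gives 0.454 and 79.4%, which round to about the stated values, and a baseline-SD effect with r near 0.64 gives 80% two-sided. The scale is also open. If the plan's 0.5 and 0.8 benchmarks are meant in single-measurement SDs, setting a change-SD value of 0.53 against 0.5 mixes scales, since the two coincide only at r = 0.5. Even on the less favourable reading the gap is modest (0.53 against 0.50), and power for a large effect of 0.8 is 98.8%. Finally, inferring absence from a non-significant test is weak at any detectable effect, so correcting the number does not cure that problem.

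Much of this stands. The 66% and 0.53 results depend on the reading, and 0.45 does have a traceable source. The ability to detect a large effect is not in doubt on this reading. But each reading that recovers 0.45 needs an assumption that the plan does not make. The one-sided reading also conflicts with the purpose: a test with almost no power in one direction cannot support a statement about any effects, and the exact one-sided t-test still gives only 77.7% at 0.45. The weakness of inferring absence from non-significance is a further reason not to rest that inference on 0.45.

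**Conclusion.** The concern holds. The power statement is under-specified, and on its natural reading (two-sided 5%, effect in SDs of the paired change, 30 complete pairs) it is overstated: power at 0.45 is 66% rather than 80%, and the 80% detectable effect is 0.53 rather than 0.45. That places it above the plan's own 0.5 benchmark, so the figure does not support reading a null result as evidence of small effects. The detectable effect stays below 0.5 only with a one-sided test, or with baseline-SD scaling and a correlation above about 0.55. The documents state neither. Fewer than 30 completed pairs would raise the detectable effect further.

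**What to change.** State the sidedness of the test and the SD that defines the effect size. For a two-sided test on the change scale, suggested text is: *30 completed pairs give 80% power, at two-sided 5%, to detect a mean change of 0.53 SD of the paired differences; power is 66% at 0.45 and 75% at 0.50.* If a one-sided test was intended, say so and justify the direction. If a baseline-SD effect size was intended, give and justify the assumed before-after correlation (about 0.64 is needed for 0.45).

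Note that 30 is the enrolment ceiling and that incomplete pairs raise the detectable effect. Remove the argument that the 0.45 figure lets non-significance show that effects are small.

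The cost is a few sentences and a slightly less favourable stated detectable effect. Restating the figure requires no added enrolment and no change to the paired t-tests. Only if the sponsor wants to keep 80% power for 0.50 in change SDs does the ceiling become an issue, since that takes 34 completed pairs.
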